15.1 Adverse Events

All adverse events will be summarized overall as well as by Run-in period and per treatment sequence by period, Microgynon alone, Microgynon + Cladribine, Microgynon + Placebo and overall.

For subjects assigned to treatment sequence 1, cladribine-placebo (see also Section 1.2 of the study protocol), the following treatment labels will be used in tables and listings:

- Run-in Period: From run-in period until Day 1 of period 1, pre-dose to Microgynon
 - In case of missing AE time on Day 1 of run-in period, the AE will be assigned to Run-in Period.
- Microgynon alone: From Day 1 of period 1, post-dose to Microgynon until Day 9 of period 1, pre-dose of Cladribine
 - o In case of missing AE time on Day 1 of period 1, the AE will be assigned to Microgynon alone
- Microgynon + Cladribine: From Day 9 of period 1, post-dose to Cladribine until Day 1 of period 2, pre-dose of Microgynon
 - In case of missing AE time on Day 9 of period 1, the AE will be assigned to Microgynon + Cladribine
 - In case of missing AE time on Day 1 of period 2, the AE will be assigned to Microgynon + Cladribine
- Microgynon alone: From Day 1 of period 2, post-dose to Microgynon until Day 9 of period 2, pre-dose of Placebo
- Microgynon + Placebo: From Day 9 of period 2, post-dose to Placebo until Day 15 of period 2, pre-dose of Cladribine
 - In case of missing AE time on Day 9 of period 2, the AE will be assigned to Microgynon + Placebo
- Microgynon + Cladribine: From Day 15 of period 2, post-dose to Cladribine until end of study.
 - In case of missing AE time on Day 15 of period 2, the AE will be assigned to Microgynon + Cladribine

Object No.

Global Version ID:

For subjects assigned to treatment sequence 2, placebo-cladribine, the following treatment labels will be used in tables and listings:

- Run-in Period: From run-in period until Day 1 of period 1, pre-dose to Microgynon
 - In case of missing AE time on Day 1 of run-in period, the AE will be assigned to Run-in Period.
- Microgynon alone: From Day 1 of period 1, post-dose to Microgynon until Day 9 of period 1, pre-dose of Placebo
 - In case of missing AE time on Day 1 of period 1, the AE will be assigned to Microgynon alone
- Microgynon + Placebo: From Day 9 of period 1, post-dose to Placebo until Day 1 of period 2, pre-dose of Microgynon
 - In case of missing AE time on Day 9 of period 1, the AE will be assigned to Microgynon + Placebo

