 - In case of missing AE time on Day 1 of period 2, the AE will be assigned to Microgynon + Placebo
- Microgynon alone: From Day 1 of period 2, post-dose to Microgynon until Day 9 of period 2, pre-dose of Cladribine
 - Microgynon + Cladribine: From Day 9 of period 2, post-dose to Cladribine until end of study. In case of missing AE time on Day 9 of period 2, the AE will be assigned to Microgynon+Cladribine

The number and percentage of subjects experiencing at least one TEAE will be summarized by treatment as well as the number of events. A TEAE is an AE with onset after start of treatment. Start of treatment defines the minimum date of first intake of microgynon or cladribine or placebo. Tables by relationship to trial drug and by severity will be generated. AEs will be coded using Medical Dictionary for Regulatory Activities terminology, latest version.

If an event was reported more than once, the worst severity will be tabulated.

Incomplete TEAE-related dates will be handled as follows:

- In case the onset date is missing completely or missing partially but the onset month and year, or the onset year are equal to the start of trial treatment then the onset date will be replaced by the minimum of start of trial treatment and TEAE resolution date.
- In all other cases the missing onset day or missing onset month will be replaced by 1.

- Incomplete stop dates will be replaced by the last day of the month (if day is missing only), if not resulting in a date later than the date of subject's death. In the latter case, the date of death will be used to impute the incomplete stop date.
- In all other cases the incomplete stop date will not be imputed.

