In addition, the following tables will be provided. Group/SOC terms will be sorted alphabetically and PTs within each group/SOC term will be sorted by descending frequency (based on all treatment groups combined):

- A table by severity of TEAEs with the number and percentage of subjects by treatment with at least one TEAE and the number of events by SOC and PT.
- A table by relationship to trial treatment (either MS treatment or microgynon) with the number and percentage of subjects by treatment with at least one TEAE and the number of events by SOC and PT.
- A table by relationship to MS treatment with the number and percentage of subjects by treatment with at least one TEAE and the number of events by SOC and PT.
- A table by relationship to microgynon with the number and percentage of subjects by treatment with at least one TEAE and the number of events by SOC and PT.

Pre-treatment AEs (AEs with onset after informed consent but before start of treatment) and TEAEs will be listed separately.

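### An adverse event with onset equal to the start of treatment is neither treatment-emergent nor pre-treatment in the SAP, and the SAP's own imputation rule creates such onsets

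*SAP*

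**What the plan says.** SAP Section 15.1 sets the TEAE boundary in two sentences: "A TEAE is an AE with onset after start of treatment. Start of treatment defines the minimum date of first intake of microgynon". The second sentence goes on to name cladribine and placebo as well. By design the earliest of these intakes is the Microgynon tablet on Run-in Day 1.

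Section 15.1.1 gives the other class: "Pre-treatment AEs (AEs with onset after informed consent but before start of treatment) and TEAEs will be listed separately".

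For incomplete onset dates, the first rule in Section 15.1 opens with "In case the onset date is missing completely or missing partially but the onset month and year, or the onset year are equal" to those of treatment start. The onset is then "replaced by the minimum of start of trial treatment and TEAE resolution date". In all other cases a missing day or month is set to 1.

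Section 15.1 also has a rule for untimed events on the first day: "In case of missing AE time on Day 1 of run-in period, the AE will be assigned to Run-in Period". It assigns a period label and does not mention TEAE status.

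The protocol does not define a TEAE. Its time frame for the safety endpoint (Section 3, Table 1) begins at first treatment.

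**The concern.** One class requires onset strictly after the start of treatment and the other strictly before it. No rule covers equality. Equality is not a remote case, because the first imputation rule sets onset to the start itself in most situations it handles. That rule belongs to a block on incomplete dates of TEAEs, so its evident purpose is to keep such events among the TEAEs. Read literally, it takes them out.

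Occurrence of TEAEs is the first-listed outcome under the secondary safety objective. The overview, severity, relationship and SOC/PT tables in Section 15.1.1 all depend on TEAE status. A programmer must choose between a strict and an inclusive comparison without guidance, and an independent check could choose differently.

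The point concerns TEAE status only, not which treatment column an event is placed in.

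**Working it through.** The plan states no figure here, so the check applies the rules as written.

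**Rules.** Let S be the start of treatment, O the onset and R the resolution date.
- TEAE (Section 15.1): O > S
- Pre-treatment AE (Section 15.1.1): O < S
- First imputation rule (Section 15.1): O = min(S, R), or O = S if the event is ongoing

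Since min(S, R) ≤ S, no onset imputed by this rule can satisfy O > S. If R ≥ S or the event is ongoing, then O = S and the event is in neither class. If R < S, then O = R and the event is pre-treatment, which is correct.

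**Test events.** S is set, as an example, to 10 March 2021 at 08:00, so Period 2 Day 12 is 16 May 2021. A match on year alone is taken to apply only when the month is also missing.

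| Event | Onset used | As written, by date | By date and time | Proposed rule |
|---|---|---|---|---|
| Day before, 20:00 | 9 March | Pre-treatment | Pre-treatment | Pre-treatment |
| Day 1, 07:00 (before tablet) | 10 March | Neither | Pre-treatment | Pre-treatment |
| Day 1, 10:00 (after tablet) | 10 March | Neither | TEAE | TEAE |
| Day 1, no time | 10 March | Neither | Not determined | TEAE |
| Day 2, 01:00 | 11 March | TEAE | TEAE | TEAE |
| Onset wholly missing, ongoing | 10 March | Neither | Neither | TEAE |
| Onset wholly missing, resolved 16 May | 10 March | Neither | Neither | TEAE |
| Year 2021 only, resolved 16 May | 10 March | Neither | Neither | TEAE |
| March 2021, day missing, resolved 30 March | 10 March | Neither | Neither | TEAE |
| March 2021, day missing, resolved 5 March | 5 March | Pre-treatment | Pre-treatment | Pre-treatment |
| April 2021, day missing | 1 April | TEAE | TEAE | TEAE |

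Imputed-to-start events fail on both readings, because the imputed onset is the start itself. Timed Day 1 events fail only on the date reading. Under the proposed rule each event falls in exactly one class.

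**Where the unclassified events still appear.** Section 15.1 also summarizes all adverse events. The SAE outputs (Section 15.2.2) and the AESI listing (Section 15.2.3.1) carry no TEAE condition. The loss is therefore from the TEAE tables and the two listings in Section 15.1.1.

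**Illustrative size of the Day 1 part, date reading only.** Three 28-day cycles are 84 × 24 = 2,016 hours. Microgynon is taken between 07:00 and 09:00 (Protocol Section 6.6.3), which leaves 15 to 17 post-dose hours on Day 1. With uniform onset the share is 15/2,016 = 0.7% to 17/2,016 = 0.8%. The documents give no frequency of missing onset dates, so the imputed part cannot be sized.

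**The case against.** The strongest reply is that the intent is clear and the SAP works with clock times. Section 9 computes time since last dose in days, hours and minutes for treatment-emergent events. Its date-only fallback gives 1 for an untimed event on a dosing day, so TEAEs on dosing days are expected. Section 15.1 splits periods at pre-dose and post-dose. On that reading, nausea two hours after the first tablet is a TEAE. This stands for timed Day 1 events. It does not settle untimed ones, and it does not help imputed onsets.

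Run-in Day 1 also precedes randomization and any cladribine or placebo, so true first-day events concern Microgynon alone, whereas the safety objective is about co-administration. That stands too, but an undated event from a cladribine period is imputed to the same start and is lost in the same way. Primary PK is unaffected.

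Three stronger readings are tempting and are not supported:
- A reader might infer that these events disappear from every output. The all-AE summary and the SAE and AESI outputs would still show them.
- A reader might infer that everything handled by the first imputation rule is lost. Events that resolved before treatment become pre-treatment, as they should.
- A reader might take 1/84 = 1.2% as a minimum share affected. It counts the whole of Day 1, including hours before the tablet, assumes uniform onset, and applies only if clock times are ignored.

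**Conclusion.** The definitions leave a gap at equality, and the first imputation rule sends events into it. This is firm for events imputed to the start of treatment, whichever way time is handled, and for untimed events on Run-in Day 1. It is conditional for timed post-dose Day 1 events, which are affected only if the start is applied as a bare date.

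The number of events is unknown and probably small. A reader might conclude that TEAE counts will be biased, but that depends on a programmer following the letter over the evident purpose, and on how many onsets are undated or untimed. What can be said is the direction: literal use only removes events from the TEAE counts. Elsewhere the SAP includes the first day, both for concomitant treatments (Section 12) and for relative study day (Section 9), so the TEAE boundary looks like a drafting slip. It is worth correcting because the rule as written works against its own purpose.

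**What to change.** In SAP Section 15.1, define a TEAE as an adverse event that starts on or after the first intake of Microgynon, cladribine or placebo, compared by date and time when both are recorded. Add that an event on that date with no recorded time, or with its onset imputed to that date, counts as a TEAE. All earlier onsets are pre-treatment, so Section 15.1.1 can keep its wording and the two classes cover every event after consent.

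The cost is a short wording change in the SAP and one comparison operator in the program, with a time check for timed first-day events. The downside is that a few untimed first-day events that began before the tablet may be counted as TEAEs. The change settles TEAE status only and leaves the period and treatment labels as they are.

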8.2 Safety Assessments and Procedures

The safety profile of the study intervention will be assessed through the recording, reporting and analysis of baseline medical conditions, adverse events (AEs), physical examination findings, vital signs, electrocardiograms, and laboratory tests.

Comprehensive assessment of any potential AE experienced by each participant will be conducted starting when the participants give informed consent and throughout the study. The Investigator will report any AEs, whether observed by the Investigator or reported by the participant; the reporting period is specified in Section [8.3.1](#) (Time Period and Frequency for Collecting Adverse Event and Serious Adverse Event Information).

For cladribine tablets an established safety and adverse event (AE) profile is available, which is based on a complete clinical development program in RMS participants. Adverse reactions described in the list below are derived from pooled data from clinical studies in RMS in which oral cladribine was used as monotherapy at a cumulative dose of 3.5 mg/kg. The safety database from these studies comprises 923 participants.

The following definitions apply to the frequency terminology used hereafter:

- very common ($\geq 1/10$);
- common ($\geq 1/100$ to $< 1/10$); uncommon ($\geq 1/1,000$ to $< 1/100$);
- rare ($\geq 1/10,000$ to $< 1/1,000$);
- very rare ($< 1/10,000$);
- frequency not known (cannot be estimated from the available data).

Infections and infestations

- Common: Oral herpes, dermatomal herpes zoster
- Very rare: Tuberculosis

Blood and lymphatic system disorders

- Very common: Lymphopenia
- Common: Decrease in neutrophil count

Skin and subcutaneous tissue disorders

- Common: Rash, alopecia

Safety & Tolerability of Microgynon

The decision to use Microgynon should take into consideration the individual woman's current risk factors, particularly those for venous thromboembolism (VTE). This risk is adequately managed by application of respective Inclusion and Exclusion Criteria as detailed in Section 5.

However, there are medical reasons for which the Investigator must stop the treatment with Microgynon immediately:

- Occurrence for the first time, or exacerbation, of migrainous headaches or unusually frequent or unusually severe headaches
- Sudden disturbances of vision, of hearing or other perceptual disorders

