- First signs of thrombosis or blood clots (e.g., unusual pains in or swelling of the leg(s), stabbing pains on breathing or coughing for no apparent reason). Feeling of pain and tightness in the chest
- 6 weeks before an elective major operation (e.g., abdominal, orthopedic), any surgery to the legs, medical treatment for varicose veins or prolonged immobilization, e.g., after accidents or surgery. Do not restart until 2 weeks after full ambulation. In case of emergency surgery, thrombotic prophylaxis is usually indicated e.g., subcutaneous heparin
- Onset of jaundice, hepatitis, itching of the whole body
- Significant rise in blood pressure
- Severe upper abdominal pain or liver enlargement
- Clear exacerbation of conditions known to be capable of deteriorating during oral contraception or pregnancy.

When stopping the oral contraception with Microgynon during the study highly effective non-hormonal contraception should be used to ensure contraceptive protection is maintained.

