8.3 Adverse Events and Serious Adverse Events

The definitions of an adverse event (AE), a serious adverse event (SAE), and adverse event of special interest (AESI) are in [Appendix 4](#).

8.3.1 Time Period and Frequency for Collecting Adverse Event and Serious Adverse Event Information

The AE reporting period for safety surveillance begins when the participant is initially included in the study (date of first signature of first informed consent) and continues until the End of Study Visit.

Any SAE assessed as related to study intervention must be recorded and reported, as indicated in [Appendix 4](#), whenever it occurs, irrespective of the time elapsed since the last administration of study intervention.

The method of recording, evaluating, and assessing causality of AEs (including SAEs) and the procedures for completing and transmitting SAE reports are presented in [Appendix 4](#).

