10.1 Disposition of Subjects and Discontinuations

This following will be presented in a summary table:

- Total number of subjects screened (ie, subjects who gave informed consent)
- Total number of subjects enrolled
- Total number of subjects randomized
- Number of screened subjects who discontinued from the trial prior to treatment overall and grouped by the main reason for discontinuation:
 - Subject did not meet all eligibility criteria
 - Withdrew consent
 - o Other (COVID-19-related and COVID-19-non-related)
- Number of treated subjects overall
- Number and percentage of treated subjects who completed study
- Number and percentage of treated subjects who discontinued the study, with the primary reason of discontinuation:
 - Adverse event

Document No.

Object No.

Global Version ID:

- Lost to follow-up
- Protocol non-compliance
- Death
- Withdrew consent
- o Other (COVID-19-related and COVID-19-non-related)
- Number and percentage of treated subjects who completed microgynon treatment
- Number and percentage of subjects who discontinued microgynon treatment with the primary reason of discontinuation
- Number and percentage of treated subjects who completed MS treatment

Number and percentage of subjects who discontinued MS treatment with the primary reason of discontinuation.

A listing of discontinued subjects will be provided.

A listing of participants affected by the COVID-19 related study disruption by unique subject number identifier will also be provided.

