15.1.1 All Adverse Events

All AEs recorded during the course of the trial (ie, assessed from signature of informed consent until the end of the Follow-up/End of Trial visit) will be coded according to MedDRA latest version and assigned to a SOC and PT.

TEAEs will be summarized by severity, using MedDRA latest version preferred term as event category and MedDRA primary system organ class (SOC) body term as Body System category.

The severity of AEs is assessed by the investigator per the Qualitative Toxicity Scale, as follows:

Mild: The participant is aware of the event or symptom, but the event or symptom is

easily tolerated.

Moderate: The participant experiences sufficient discomfort to interfere with or reduce his or

her usual level of activity.

Severe: Significant impairment of functioning: the participant is unable to carry out his or

her usual activities.

TEAEs related to trial treatment are those events with relationship missing, unknown or related.

The following will be summarized in an overview table with the number and percentage of subjects (and the number of events).

- Any TEAE
- TEAEs of special interest
- Trial treatment (either MS treatment or microgynon) related TEAEs
- MS treatment related TEAEs
- Microgynon related TEAEs
- Any serious TEAEs
- Trial treatment (either MS treatment or microgynon) related serious TEAEs
- MS treatment related serious TEAEs

- Microgynon related serious TEAEs
- Any severe TEAE
- Trial treatment (either MS treatment or microgynon) related severe TEAE
- MS treatment related severe TEAE
- Microgynon related severe TEAE
- TEAEs leading to death
- Trial treatment (either MS treatment or microgynon) related TEAEs leading to death
- MS treatment related TEAEs leading to death
- Microgynon related TEAEs leading to death

TEAEs will be summarized in tables with:

- The number and percentage of subjects by treatment with at least one TEAE and the number of events overall and by SOC and PT. Group/SOC terms will be sorted alphabetically and PTs within each group/SOC term will be sorted by descending frequency.
- The number and percentage of subjects by treatment with at least one non-serious TEAE and the number of non-serious TEAE applying frequency threshold of 5%. Group/SOC terms will be sorted alphabetically and PTs within each group/SOC term will be sorted by descending frequency.

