15.1.2 Adverse Events Leading to Treatment Discontinuation

TEAEs leading to permanent discontinuation of trial treatment will be summarized including number of subjects, percentage and number of events.

A listing of TEAEs leading to permanent discontinuation of a trial treatment will additionally be provided.

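### The SAP's onset-only TEAE definition misses an adverse event that begins in screening and worsens on treatment, if the site keeps it as one record with its screening onset date.

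*SAP*

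**What the plan says.** SAP 15.1 gives the definition: "A TEAE is an AE with onset after start of treatment". It takes the earliest intake of Microgynon, cladribine or placebo as the start of treatment. Under Protocol 6.6.3 that is the first Microgynon tablet of the run-in, so screening is the pre-treatment phase and run-in events already count as TEAEs.

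SAP 15.1.1 applies the same onset test on the other side of the boundary: "Pre-treatment AEs (AEs with onset after informed consent but before start of treatment) and TEAEs will be listed separately". SAP 15.1.2 limits the discontinuation output to TEAEs: "TEAEs leading to permanent discontinuation of trial treatment will be summarized including number of subjects, percentage and number of events". Its accompanying listing is limited in the same way. Disposition in SAP 10.1 has no such limit: "Number and percentage of subjects who discontinued microgynon treatment with the primary reason of discontinuation".

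AEs are collected during screening. Protocol 8.3.1 says: "The AE reporting period for safety surveillance begins when the participant is initially included in the study", which it ties to the first consent signature. Protocol 8.2.1 sends findings from before consent to the medical history form. Current findings go to the AE form, including those unresolved when study treatment starts. The protocol uses the term TEAE without defining it, and neither document adds a worsening clause.

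**The concern.** A usual TEAE definition has two limbs: new onset after first dose, or worsening after first dose of something already present. The SAP has only the first. An event recorded in screening that becomes worse on Microgynon or cladribine could therefore stay classed as pre-treatment for the whole study.

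Occurrence of TEAEs is the first endpoint named under the safety objective. At stake is whether the TEAE tables count every non-serious deterioration on treatment, and whether the discontinuation table agrees with disposition. A woman whose headache began in screening, worsened on Microgynon and led to stopping it could be a discontinuation in SAP 10.1 and absent from SAP 15.1.2.

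**Working it through.** There is no planned figure to reproduce. The check applies the written rules to each way in which a worsening can reach the database.

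| Case | Recorded onset | Class under SAP 15.1 and 15.1.1 | In TEAE tables? |
|---|---|---|---|
| A. AE starts in the run-in or later | After first tablet | TEAE | Yes |
| B. Condition predates consent, worsens on treatment | Normally the worsening, because Protocol Appendix 4 exempts a baseline condition from being an AE only while it does not worsen | TEAE | Usually yes |
| C. AE starts between consent and first tablet; worsening entered as a new AE | After first tablet | TEAE | Yes |
| D. As C, but kept as one record | Screening | Pre-treatment AE | No |

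Only case D is affected. Its event is missing from the overview, SOC/PT, non-serious, severity and relationship tables in SAP 15.1.1, and from the summary and listing in SAP 15.1.2. It remains in the pre-treatment AE listing and, if it ends treatment, in disposition and the listing of discontinued subjects. If serious, it is in the SAE table (SAP 15.2.2). Grade 3 or 4 lymphopenia is in the AESI listing (SAP 15.2.3.1). Neither of those two outputs is limited to TEAEs. The uncounted part is therefore non-serious worsening.

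Other SAP rules do not bring case D back:

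- The worst-severity rule in SAP 15.1 decides which grade is tabulated, not whether the event is a TEAE.
- Date imputation in SAP 15.1 acts only on missing or partial onset dates.
- SAP 9 computes duration across several records of one AE, but does not say which record's onset decides treatment emergence.
- SAP 15.1 opens by saying that all AEs are summarized, but its treatment labels begin at the run-in. Laboratory data and vital signs have a screening label (SAP 15.3 and 15.4); AEs do not.

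Time windows, from Protocol 4.1:

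- Onset: screening of up to 21 days, or up to 60 days with a delayed cycle. Laboratory retesting can also prolong screening.
- Worsening: from the first tablet (day 1) to the End of Study visit, at day 28 + 28 + 21 + 4 = 81 to day 28 + 28 + 21 + 7 = 84.

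Scale of one woman, as an assumption because planned enrolment is redacted: Protocol 7.2 gives 16 evaluable and 18% to 30% drop-out. This implies 16/(1 - 0.18) = 19.5, so 20, to 16/(1 - 0.30) = 22.9, so 23. One woman is 1/16 = 6.25 points at the lower bound and 1/23 = 4.3 points at the upper. The 16 is a PK count used only as a floor; the Safety Set includes anyone with one dose.

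**The case against.** The strongest objection is Protocol 8.3.2, under which any unfavorable change in a participant's condition during the reporting period is to be recorded as an AE. A worsening is such a change, so the natural reading is a new record dated on treatment: case C, which counts. This largely stands. A reader might infer that every screening-onset AE that worsens drops out of every TEAE table; the documents do not support that. They do not exclude case D either. Protocol 8.3.2 does not state the onset date, the SAP foresees several records for one AE, and Protocol Appendix 4 leaves recording detail to CRF conventions outside both documents.

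A reader might also take the Microgynon stopping rules in Protocol 8.2 as proof that the plan expects the missing events. They name "Occurrence for the first time, or exacerbation, of migrainous headaches" and "Clear exacerbation of conditions known to be capable of deteriorating during oral contraception or pregnancy". Most such conditions would predate consent, go to medical history, and become AEs only on worsening: case B. The rules show that worsening matters clinically, but not that it is generally lost.

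Third, the SAP tabulates subjects with "at least one non-serious TEAE and the number of non-serious TEAE applying frequency threshold of 5" per cent, which invites the inference that one uncounted woman removes a term. If the threshold means at least 5%, one woman meets it at 20 (1/20 = 5.0%) but not at 21 (1/21 = 4.8%). The arithmetic is right, but it holds for any single AE and is not evidence of an effect.

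Finally, the remedy is uneven. A screening-onset AE that worsens on cladribine would be labelled by its worsening, while a run-in AE that worsens on cladribine keeps its onset label. That is true, but the run-in AE is already a TEAE, and its attribution is a separate matter.

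**Conclusion.** The definition is incomplete, and the gap is narrow. It affects non-serious AEs that first appear between consent and the first Microgynon tablet, worsen afterwards, and are kept as one record with the screening onset date. Those worsenings are left out of the TEAE tables and the TEAE-only discontinuation outputs, so SAP 15.1.2 can disagree with SAP 10.1.

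The conclusion assumes that the CRF conventions do not already require a new record; if they do, the gap closes in practice. The number of affected AEs cannot be derived from the documents and is probably small. The events stay visible in the pre-treatment listing, the safety tables are descriptive, and the primary PK analysis is unaffected. This is a minor improvement worth making because it is cheap.

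**What to change.** In SAP 15.1, define a TEAE as an AE with onset, or a worsening in severity or frequency of a pre-treatment AE, after first intake of Microgynon, cladribine or placebo. Use the same definition for the pre-treatment and TEAE listings in 15.1.1 and for both outputs in 15.1.2.

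Implement it by instructing sites to enter the worsening of a pre-treatment AE as a new AE record with its own onset date. The existing treatment labels then apply and no new eCRF field is needed. State that combining records for duration under SAP 9 does not alter TEAE status. Leave attribution by onset unchanged for AEs that start on treatment.

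The cost is one SAP clause, one line in the CRF completion guidance, minor programming, and possible queries on records already entered. TEAE counts may rise slightly.
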